Any component of a study endpoint that is considered related to study therapy should be reported as an SAE (eg, death is an endpoint, if death occurred due to anaphylaxis, anaphylaxis must be reported).

NOTE: (PI determines if this information regarding hospitalizations are considered SAEs and should be included in the protocol. This is supplemental information that is included in BMS-sponsored trials)

The following hospitalizations are not considered SAEs in BMS clinical studies:

- a visit to the emergency room or other hospital department < 24 hours, that does not result in admission (unless considered an important medical or life-threatening event)
- elective surgery, planned prior to signing consent
- admissions as per protocol for a planned medical/surgical procedure
- routine health assessment requiring admission for baseline/trending of health status (eg, routine colonoscopy)
- Medical/surgical admission other than to remedy ill health and planned prior to entry into the study. Appropriate documentation is required in these cases.

- Admission encountered for another life circumstance that carries no bearing on health status and requires no medical/surgical intervention (eg, lack of housing, economic inadequacy, caregiver respite, family circumstances, administrative reason).
- Admission for administration of anticancer therapy in the absence of any other SAEs (applies to oncology protocols)

ADVERSE EVENTS

An Adverse Event (AE) is defined as any new untoward medical occurrence or worsening of a preexisting medical condition in a clinical investigation participant administered study drug and that does not necessarily have a causal relationship with this treatment. An AE can therefore be any unfavorable and unintended sign (such as an abnormal laboratory finding), symptom, or disease temporally associated with the use of investigational product, whether or not considered related to the investigational product.

The causal relationship to study drug is determined by a physician and should be used to assess all adverse events (AE). The causal relationship can be one of the following:

Related: There is a reasonable causal relationship between study drug administration and the AE.

Not related: There is not a reasonable causal relationship between study drug administration and the AE.

The term "reasonable causal relationship" means there is evidence to suggest a causal relationship.

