Adverse events can be spontaneously reported or elicited during open-ended questioning, examination, or evaluation of a subject. (In order to prevent reporting bias, subjects should not be questioned regarding the specific occurrence of one or more AEs.)

NONSERIOUS ADVERSE EVENT

- Non-serious Adverse Events (AE) are to be provided to BMS in aggregate via interim or final study reports as specified in the agreement or, if a regulatory requirement [eg, IND US trial] as part of an annual reporting requirement.
- Non-serious AE information should also be collected from the start of a placebo lead-in period or other observational period intended to establish a baseline status for the subjects.

A *non-serious adverse event* is an AE not classified as serious.

Non-serious Adverse Event Collection and Reporting

The collection of non-serious AE information should begin at initiation of study drug. All non-serious adverse events (not only those deemed to be treatment-related) should be collected continuously during the treatment period and for a minimum of 30 days following the last dose of study treatment.

Non-serious AEs should be followed to resolution or stabilization, or reported as SAEs if they become serious. Follow-up is also required for non-serious AEs that cause interruption or discontinuation of study drug and for those present at the end of study treatment as appropriate.

Laboratory Test Abnormalities

All laboratory test results captured as part of the study should be recorded following institutional procedures. Test results that constitute SAEs should be documented and reported to BMS as such.

The following laboratory abnormalities should be documented and reported appropriately:

- any laboratory test result that is clinically significant or meets the definition of an SAE
- any laboratory abnormality that required the participant to have study drug discontinued or interrupted
- any laboratory abnormality that required the subject to receive specific corrective therapy.

It is expected that wherever possible, the clinical rather than laboratory term would be used by the reporting investigator (eg, anemia versus low hemoglobin value).

Potential Drug Induced Liver Injury (DILI)

Potential drug induced liver injury is defined as:

- 1) AT (ALT or AST) elevation > 3 times upper limit of normal (ULN)

AND

- 2) Total bilirubin > 2 times ULN, without initial findings of cholestasis (elevated serum alkaline phosphatase)

AND

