Chemistry: Blood (5.0 mL) will be collected into a serum gel (SST) tube.

Hepatitis serologies (HBsAg, HBcAb, HCVAb): Blood (4.0 mL) will be collected into a serum gel (SST) tube. Immunoglobulins (IgG, IgM, IgE, IgG4) and Complement C3 and C4: Blood (5 mL) will be collected into a serum gel (SST) tube.

Flow Cytometry B Cell and CD19 RO: Blood (3.0 mL) will be collected into a lavender-top tube and blood (5.0 mL) will be collected in a Cyto-Chex BCT glass streck CE marked tube.

Plasmablast and CD4+ CTL Assessment: Blood (5.0 mL) will be collected in a Cyto-Chex BCT glass streck CE marked tube.

Laboratory Values Outside Normal Range:

Any value outside the normal range will be flagged for the attention of the Investigator or designee at the site. The Investigator or designee will indicate whether or not the value is of clinical significance. Laboratory values that are clinically significant and that are not explained by the subject's underlying disease or medications should be entered as AEs and the relationship to study drug assigned. A laboratory value of clinical significance typically requires a diagnostic or therapeutic intervention other than repeating the test. Additional testing during the study may be done if medically indicated. The study subject will be followed until the test(s) has (have) normalized or stabilized.

Physical Examination

Complete physical examinations will be performed at Screening, on Day 1 (could potentially be the same visit) and at EOS. Abbreviated PEs will be directed towards the symptoms of IgG4-RD that were previously defined and will be performed at all other visits.

The physical examination includes an assessment of general appearance and a review of systems (dermatologic, head, eyes, ears, nose, mouth/throat/neck, thyroid, lymph nodes, respiratory, cardiovascular, gastrointestinal, extremities, musculoskeletal, neurologic, and psychiatric systems).

Vital Signs

Vital signs will be assessed at Screening (Visit 1) and at each visit to the PI's office. The following vital signs will be measured:

- Blood pressure (systolic and diastolic [mmHg]);
- Heart rate (beats per minute [bpm]);
- Body temperature (°C);
- Respiratory rate (breaths per minute).

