8.2 Endpoints

Primary Efficacy Endpoint

The primary endpoint is complete remission at 24 weeks. Complete remission is defined as an IgG4-RD Responder Index Score of 0 and a prednisone dose of 0 mg/day and no flare since beginning treatment.

Secondary Efficacy Endpoints

- Disease response at 4, 12, 24, and 36 weeks. Disease response will be defined at 6 months as: 1) improvement of ≥ 1 point in the IgG4-RD RI score over baseline; 2) no glucocorticoid use following the week 4 visit; 3) no disease flares, as assessed by the IgG4-RD RI. Disease flare will be defined as recurrence of disease activity or demonstration of a disease exacerbation such that additional therapy beyond the trial protocol is indicated. Such additional therapy may include glucocorticoids or alternative immunosuppressive agents.
- Complete remission at 36 weeks.
- Time to disease remission (IgG4-RD RI = 0)
- Remission rates

- Number of disease flares per subject over time
- Cumulative corticosteroid doses and Glucocorticoid Toxicity Index
- Physician Global Assessment (PGA). A PGA consisting of a 10-centimeter visual analog scale is collected at each patient visit. Only active disease (as opposed to damage) is considered in the scoring of the PGA.
- Symptom Severity Index
- Serum immunoglobulin levels, IgG4 subclass concentrations, IgE levels, eosinophils, and serum C3 and C4

Safety Endpoints

Safety analyses will be performed using all treated subjects.

- The number and percent of subjects experiencing a treatment-emergent adverse event will be tabulated for each coded MedDRA system-organ class and preferred term. Treatment-emergent adverse events will also be tabulated according to intensity and causality.
- All SAEs, discontinuations due to AE, or deaths occurring during the course of the trial will be presented in subject listings.
- The number and percent of subjects experiencing a glucocorticoid-related AE will be tabulated for each coded MedDRA system-organ class and preferred term. Treatment-emergent adverse events will also be tabulated according to intensity and causality.

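### The rule for turning laboratory values into AEs filters on cause, contradicting the protocol's cause-blind AE definition and letting prednisone-attributed changes escape the glucocorticoid-related AE endpoint

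*Protocol*

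**What the plan says.** All the recording rules at issue stand in section 7.3 of the protocol.

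- **Laboratory Values Outside Normal Range** sets the entry rule for laboratory AEs: "Laboratory values that are clinically significant and that are not explained by the subject's underlying disease or medications should be entered as AEs". The same sentence then asks for the relationship to study drug.
- **Adverse Events** (definition): "An AE can therefore be any unfavorable and unintended sign (such as an abnormal laboratory finding), symptom, or disease temporally associated" with use of the product, "whether or not considered related to the investigational product". The definition also covers "worsening of a preexisting medical condition in a clinical investigation participant administered study drug".
- **Non-serious Adverse Event Collection and Reporting**: "All non-serious adverse events (not only those deemed to be treatment-related) should be collected continuously during the treatment period".
- **Laboratory Test Abnormalities** lists what must be documented and reported, including "any laboratory test result that is clinically significant or meets the definition of an SAE" and any abnormality that needed corrective therapy.
- **Other Safety Considerations** has significant worsening on any safety assessment recorded as a serious or non-serious AE.

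The synopsis names the incidence of corticosteroid-related AEs as a secondary safety endpoint. Section 8.2, Safety Endpoints, gives its form: "The number and percent of subjects experiencing a glucocorticoid-related AE will be tabulated", by MedDRA class and term. The same section puts laboratory abnormalities into the AE listings only where the investigator considered them AEs.

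**The concern.** The laboratory rule puts a judgement of cause before AE entry. The definition and the other rules put it after, or do not ask for it. A site therefore has two instructions for the same abnormal value.

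The conflict matters most for the glucocorticoid-related AE endpoint. A laboratory change attributed to prednisone is, by that attribution, explained by a medication. The finding that would qualify the event for the endpoint is thus the same finding that excuses the site from entering it. At stake is the completeness of a named safety endpoint in a single-arm trial of about 10 subjects, where one event more or less changes the reported incidence visibly.

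**Working it through.** The protocol states no figure on this point, so the check is textual.

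**Step 1: the rules side by side for one case.** Take a subject on prednisone whose HbA1c or fasting lipids rise to a clinically significant level during the study.

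| Rule in section 7.3 | Does cause matter? | Result for this case |
|---|---|---|
| AE definition | No | Qualifies as an AE |
| Non-serious AE collection | No | Collected once it is an AE |
| Laboratory Test Abnormalities | No | Documented and reported |
| Other Safety Considerations | No | Recorded as an AE if significantly worse |
| Laboratory Values Outside Normal Range | Yes | Need not be entered, since a medication explains it |

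The last row disagrees with the others.

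**Step 2: can the case arise?** Yes. Subjects may be on prednisone at baseline and taper it (section 6.3), and steroids may be given again later (section 5, Description). Glucose and HbA1c are in the chemistry panel, and fasting lipids and HbA1c are drawn at the visits where the Glucocorticoid Toxicity Index is scored (section 7.3, Laboratory Assessments). HbA1c meets the filter from two sides: the protocol also uses it as a surrogate for pancreatic endocrine function, which section 3.3 says IgG4-RD can damage. Whether a rise is put down to the disease or to prednisone, the rule excuses entry.

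**Step 3: does the analysis recover the event?** Not in the AE tables. By section 8.2, laboratory abnormalities reach the AE listings only if the investigator considered them AEs. An event not entered cannot be counted in the glucocorticoid-related table.

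**Step 4: scale.** Let N be the number of treated subjects and k the number whose only glucocorticoid-related AE is a laboratory change left out under the filter. The incidence falls by k/N. With N = 10 (the planned number is approximate):

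- k = 0: 0/10 = 0 percentage points
- k = 1: 1/10 = 10 percentage points
- k = 2: 2/10 = 20 percentage points

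The protocol gives neither the expected number of subjects on prednisone nor a rate of such events. These values of k are therefore illustrations, and the actual loss cannot be computed.

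**The case against.** The strongest reply is that the laboratory rule says what to enter and does not forbid entering more. A site that follows the AE definition, the collection rule and the rule on worsening would still record these events. Abnormalities that needed corrective therapy must be documented and reported in any case, and the protocol prefers a clinical term to a laboratory term, so steroid-induced diabetes could be entered as a diagnosis. This stands: the fault is inconsistent capture, not certain loss. Two of the competing texts are also softer than they look. The definition says that an abnormal laboratory finding can be an AE, and the laboratory reporting list does not say that each item is reported as an AE.

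It also stands that the data are not lost. Section 8.2 plans summaries of observed values, shift tables for select parameters, and listings of out-of-range values with the investigator's judgement of significance. Glucose tolerance and lipids are scored in the Glucocorticoid Toxicity Index, itself a secondary endpoint. None of these, however, gives the MedDRA-coded incidence by subject that section 8.2 promises.

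A reader might infer three stronger points that the protocol does not support.

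- *That changes caused by abatacept are also screened out.* The sentence goes on to ask for the relationship to study drug, which would be pointless if the medications meant included abatacept. Other medications are the natural reading.
- *That glucocorticoid attribution has nowhere to be recorded.* The protocol defines causality only for study drug, but the AE form is not shown, and a SAP or case report form may settle how these events are identified.
- *That the weight of glucose and lipids in the Glucocorticoid Toxicity Index measures the loss.* Those weights are shares of an instrument's score, not of events or subjects.

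**Conclusion.** The point holds as an internal contradiction with a one-sided effect. The laboratory entry rule is narrower than the AE definition and the neighbouring rules. Where a site follows it, prednisone-attributed changes in glucose, HbA1c or lipids can be left out of the endpoint meant to count them. Any resulting error runs towards too low a count.

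The size is unknown. It depends on how many subjects take prednisone, how many have a significant laboratory change attributed to it, and which of the conflicting instructions the site follows. The conclusion assumes that the medications in the filter include prednisone, which nothing in the text contradicts. The primary endpoint is not affected. The correction is worth making because the wording works against a named safety endpoint and is easy to repair.

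**What to change.** Reconcile Laboratory Values Outside Normal Range with the rest of section 7.3:

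1. Strike the medications limb of the filter. Enter as an AE every clinically significant laboratory change that is new or worse than baseline, whatever medication explains it.
2. Judge cause after entry: relationship to abatacept, as now, and relationship to glucocorticoid. Build the glucocorticoid-related AE table in section 8.2 from the second judgement.
3. Limit any underlying-disease exception to the IgG4-RD activity markers already analysed as efficacy endpoints: immunoglobulins including IgG4 and IgE, eosinophils, C3 and C4. Removing the exception altogether could list disease-driven values of these markers as AEs and mix efficacy with safety.

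The cost is a short edit to one rule and, if the AE form does not already have it, one attribution item. A few more laboratory AEs will be listed. No treatment, visit or test changes.

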8. STATISTICAL EVALUATION

8.1 Analysis Population

The definitions of study populations are as follows:

- Efficacy Population: All subjects. This population will be used for the primary efficacy analysis and other efficacy analyses except where otherwise noted.
- Safety Population: All subjects treated with abatacept. This population will be used for safety analyses.
- Patient Reported Outcome Population (PRO): All randomized subjects who have a non-missing baseline and at least one post-baseline PRO assessment. Subjects in this subset will be analyzed according to their randomized treatment assignment, regardless of treatment received, except where otherwise noted.
- Pharmacokinetic Population: Subjects with at least one quantifiable trough concentration result will be included in this population.
- Pharmacodynamic Population: Subjects with a quantifiable baseline and at least one post-baseline assay result will be included in this population.
- Open-label Population: Subjects with contraindications to or who refuse glucocorticoid therapy may enter an open-label study and receive XmAb5871 if they otherwise meet all other inclusion and exclusion criteria. These subjects will follow the same schedule of assessments, but safety and efficacy will be reported separately.
- Continuing Glucocorticoid Population: Subjects who continue on study after an unsuccessful glucocorticoid taper or who continue after receiving glucocorticoid rescue therapy following a successful taper.

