5.3 Discussion of Study Design

No therapies for IgG4-RD have been approved by regulatory authorities and thus there are no established study designs for this disease indication. This study design is consistent with the focus of this trial on proof-of-concept and mechanistic studies and will be suitable to achieve this goal based on the strict primary outcome criteria. There is no control group in this proof of concept study. The design will be able to assess whether abatacept can have an effect on disease response as has been shown in a prior case report as discussed above. The design of this trial is appropriate to our current understanding of the potential role of abatacept in IgG4-RD, which is presently too limited to justify a randomized trial. Should patients fail to respond to the study drug abatacept or should they develop end-organ manifestations, they will be able to obtain standard of care glucocorticoid treatment.

A washout period is built into the study protocol. Exclusion criteria include the prior use of rituximab (or other B cell depleting agents) within 6 months of enrollment unless B cells have been demonstrated to have repopulated or the use of any investigational agent within 5 half-lives of the agent (or 6 months if the half-life is unknown) prior to enrollment. This should be sufficient in identifying any adverse effects due to the investigational product abatacept. However, patient's may have been on glucocorticoids during trial entry, but must be willing to taper off of glucocorticoids within ~~4~~ 8 weeks of beginning abatacept. This is necessary in order to sufficiently recruit patients for the study.

The investigational medication abatacept is dosed weekly by subcutaneous route which is consistent with its pharmacokinetic and pharmacodynamic profile. It is approved for the treatment of rheumatoid arthritis at this dosing interval. These medications may be continued indefinitely for control of the disease and any effect should be seen within 24 weeks of treatment.

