4. Uncontrolled disease: evidence of another uncontrolled condition, including drug and alcohol abuse, which could interfere with participation in the trial according to the protocol.
5. Presence of recurrent or chronic infections, defined as ≥ 3 infections requiring antimicrobials over the past 6 months prior to screening.

6. Active infection requiring hospitalization or treatment with parenteral antimicrobials within the 30 days prior to randomization.
7. Prior use of rituximab (or other B cell depleting agents) within 6 months of enrollment unless B cells have been demonstrated to have repopulated.
8. Use of any investigational agent within 5 half-lives of the agent (or 6 months if the half-life is unknown) prior to enrollment.
9. White blood cell count $< 2.5 \times 10^3/\mu\text{L}$.
10. Absolute neutrophil count (ANC) $< 1.0 \times 10^3/\mu\text{L}$.
11. IgG4-related renal disease with serum creatinine $> 2.0 \text{ mg/dL}$.
12. Hemoglobin $< 10 \text{ g/dL}$.
13. Platelet count $< 75 \times 10^9/\text{L}$.
14. Known positive result for HIV I or II antibody, hepatitis B surface antigen, hepatitis B core antibody or hepatitis C antibody.
15. Has received live vaccines within 4 weeks of enrollment.
16. Inability to communicate reliably with the investigator.
17. Patient is pregnant or breast feeding, or planning to become pregnant while enrolled in the study, up to EOS visit.
18. Positive pregnancy test at screening or during the study.
19. Subjects of childbearing potential who do not agree to use medically acceptable methods of contraception.
20. Known or suspected sensitivity to mammalian cell-derived products or any components of the study drug.
21. History of alcohol and/or substance abuse within 12 months prior to screening.
22. Unable or unwilling to partake in follow-up assessments or required protocol procedures.

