8.3 Quality of Life Assessments

Quality of life assessments will include the Physician Global Disease Activity Assessment Visual Analogue Scale (PhGA VAS), the Patient Global Disease Activity Assessment VAS (PtGA VAS), the Symptom Severity Index and the 36-item short form health survey (SF-36). Unless otherwise specified, the QOL analyses will include all randomized subjects who have a non-missing baseline and at least one post-baseline QOL assessment. Subjects in this subset

will be analyzed according to their randomized treatment assignment, regardless of treatment received.

The percentage of participants randomized to each treatment group who complete the QOL questionnaires at each assessment point after baseline (i.e., QOL completion rates) will be calculated and compared. If significant differences in QOL completion rates are observed, additional analyses may be performed to evaluate the potential for reporting biases.

For each QOL endpoint, descriptive statistics will be presented for recorded values at each visit, including mean, standard deviation, median, minimum, maximum, change from baseline and percent change from baseline.

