8.4 Statistical Methods General

Considerations

Summary statistics will be presented by way of n, mean, standard deviation (SD), median, minimum and maximum for continuous variables and by way of group frequencies and percentages for categorical variables. Percentages will be calculated using the total subjects per arm in the planned analysis population, unless specified otherwise.

For listings, in the cases where a subject's record has been continued to the next page, an appropriate identification (e.g., the subject ID number) must be presented at the beginning of that page.

Unless otherwise specified, in summary tables of continuous variables, the minimum and maximum values will be displayed to the same number of decimal places as the raw data, the mean and median will be presented to one extra decimal place compared to the raw data, and the standard deviation will be displayed to two extra decimal places compared to the raw data. Wherever possible, data will be decimal aligned.

Unless otherwise specified frequency tabulations will be presented by number and percentage, where the percentage is presented in brackets to 1 decimal place.

P-values, if applicable, will be presented to 3 decimal places. If a p-value is less than 0.05 but is greater than or equal to 0.01, then an asterisk (*) will be added next to this value. If a p-value is less than 0.01 but is greater than or equal to 0.001, then two asterisks (**) will be added next to this value. Finally, if the p-value is less than 0.001 then three asterisks (***) will be added next to this value and it will be presented as <0.001. If the rounded result is a value of 1.000, it will be displayed as >0.999.

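### Rules on randomised subjects, XmAb5871 and dosing after week 24 do not fit this single-arm, open-label, 24-dose abatacept trial

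*Protocol*

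**What the plan says.** The design is clear. Section 5.3 states that "There is no control group in this proof of concept study" and describes current knowledge of the drug in this disease as one "which is presently too limited to justify a randomized trial". Section 6.2 gives abatacept to everyone. The design description in Section 5 sets 24 weekly doses, with off-treatment visits at weeks 28 and 36, and 5.4 ends the study at week 36.

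Four sets of rules in the same document say something else:

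- **PRO and QOL analyses.** Section 8.1 defines the PRO population as "All randomized subjects who have a non-missing baseline and at least one post-baseline PRO assessment" and adds: "Subjects in this subset will be analyzed according to their randomized treatment assignment, regardless of treatment received, except where otherwise noted". Section 8.3 says: "Unless otherwise specified, the QOL analyses will include all randomized subjects who have a non-missing baseline and at least one post-baseline QOL assessment". It also plans to calculate and compare "The percentage of participants randomized to each treatment group who complete the QOL questionnaires at each assessment point after baseline". Section 8.4 adds: "Percentages will be calculated using the total subjects per arm in the planned analysis population, unless specified otherwise".
- **Exclusion criterion 6** (synopsis and 5.5): "Active infection requiring hospitalization or treatment with parenteral antimicrobials within the 30 days prior to randomization".
- **Open-label Population in 8.1.** Subjects who cannot or will not take glucocorticoids may enter an open-label study of XmAb5871, with safety and efficacy reported apart from the rest.
- **Section 5.2, visits 3 to 10.** Item 6 lists abatacept at baseline and weeks 4, 12, 20, 28, 36 and 44. Item 10 calls for dispensing across the same visits.

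Two smaller remnants are of the same kind: 3.3 gives 25 doses, and 5.8 speaks of unblinded analyses in a trial with no blinding.

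**The concern.** These are stated rules, not details left for an analysis plan, and they give a wrong or unworkable result if followed. Section 11.4 requires exact adherence to the protocol and an amendment for deviations, so it is not enough that staff would probably guess what was meant.

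The PRO/QOL rule reaches named endpoints. Section 8.3 places the physician global assessment and the Symptom Severity Index under it, and 8.2 lists both as secondary efficacy endpoints. Exclusion 6 is a safety criterion on recent serious infection, ahead of a drug for which 3.5 names infection among the most serious adverse events; its window has no defined end. The XmAb5871 paragraph and 6.2 give conflicting instructions for the same eligible subject, because nothing in the eligibility criteria requires glucocorticoids. The dosing list conflicts with the drug-free follow-up before the week-36 remission assessment, which is a secondary endpoint in 8.2 and the primary endpoint in the synopsis.

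**Working it through.** No sample-size or error-rate figure is involved. The check sets the rules beside the design and counts.

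**Dose count.** The study-drug row of the schedule in 5.1 has 15 marks for weeks 1 to 15 and 9 for weeks 16 to 24. 15 + 9 = 24, which reproduces the stated 24 doses. There is no mark at week 28 or 36. The 25 doses in 3.3 disagree by one.

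**PRO/QOL set.** Sections 8.1 and 8.3 use the word randomized 2 + 3 = 5 times in defining, analysing or comparing subjects. Number randomised = 0, so the literal set is 0 of about 10. If the word is read as enrolled, the set is usable, but the completion comparison needs at least 2 groups and has 1. The per-arm denominator in 8.4 then simply means the whole analysis population.

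**Exclusion 6.** The criterion needs a date from which to count back 30 days. Neighbouring criteria offer two candidates: screening (criterion 5) and enrollment (criteria 7 and 8). First dose is a third. Sections 5.1 and 5.2 say that screening and the first treatment visit may fall on one day, but do not require it. The candidate dates differ by the gap between those visits. The protocol gives no figure for that gap: if it is 0 days the choice makes no difference, and otherwise the window shifts by exactly that gap.

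**XmAb5871.** Section 8.1 allows another drug with separate reporting; 6.2 allows only abatacept. Section 6.3 applies the prednisone taper only to subjects taking prednisone at baseline, so a subject who refuses glucocorticoids can still qualify for abatacept. The two rules cannot both hold for that subject.

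**Dosing list in 5.2.**

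| Listed time | Rest of the protocol |
|---|---|
| Baseline (week 1), weeks 4, 12, 20 | Study drug marked in the schedule |
| Week 28 | Visit exists, off treatment |
| Week 36 | Visit exists, off treatment, end of study |
| Week 44 | No visit; 44 − 36 = 8 weeks after end of study |

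Three of the 7 listed times fall after the last dose at week 24. Planned drug-free interval before the week-36 assessment: 36 − 24 = 12 weeks. With a week-28 dose: 36 − 28 = 8 weeks. A week-36 dose would fall on the assessment visit itself.

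**The case against.** The strongest reply is that no reasonable reader would be misled. With one arm, randomised naturally reads as enrolled, and the descriptive statistics by visit in 8.3 can still be computed. The Efficacy Population, defined as all subjects, covers other efficacy analyses. The 5.2 list refers back to the schedule, which has no drug after week 24, and the 24-dose limit appears repeatedly. All of this lowers the practical risk. It does not remove the defect: the Efficacy Population gives way where another rule is noted, and 8.3 notes one; the between-group comparison fails on any reading; and exclusion 6 still lacks a date.

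Several stronger readings are tempting but not supported:

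- *Some subjects will be given another drug.* The wording is permissive, and the protocol contains no dose, supply, storage or safety text for XmAb5871. The paragraph could not be carried out under this protocol. The fault is the contradiction.
- *Drug will be given during the drug-free period.* Several explicit statements point the other way, so the loss of 4 weeks (12 − 8) is conditional on a site following 5.2.
- *The 5.2 list omits most of the weekly doses.* It describes clinic visits, and home self-injection is allowed, so it need not show all 24.
- *The interim efficacy rule is missing.* Section 5.8 refers to a monitoring-committee charter, and such rules may sit there or in an analysis plan not shown. Only the word unblinded is out of place.

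The choice of first dose rather than enrollment as the anchor for exclusion 6 is a matter of judgement; either works if used consistently.

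**Conclusion.** The point holds. Rules in 8.1, 8.3, exclusion 6 and 5.2 contradict the stated design and should be corrected. Its size is as follows: a literal PRO/QOL set of 0 of about 10; one group where a comparison needs two; one eligibility window without an anchor; one analysis population for a drug not otherwise in the trial; and 3 of 7 listed dosing times after the last scheduled dose.

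The primary efficacy set and the safety set are correctly defined and need no change, so no primary estimate or safety denominator moves. The dosing and XmAb5871 items are risks created by conflicting text, not expected events. The conclusion rests on these sections being current operative text, which they are. That they were carried over from another trial's protocol is likely, but it is an inference and the conclusion does not need it.

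**What to change.** Amend the text as follows:

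- **8.1 and 8.3:** define the PRO/QOL population as all subjects treated with abatacept who have a baseline and one or more later assessments. Delete the sentences on randomised assignment. Replace the between-group comparison with completion rates reported by visit.
- **8.4:** replace the per-arm denominator with the number in the analysis population.
- **Exclusion 6 (synopsis and 5.5):** count the 30 days back from the first dose of abatacept, or from enrollment, and use the same anchor in both places.
- **8.1:** delete the Open-label (XmAb5871) Population.
- **5.2 item 6:** state abatacept 125 mg SC weekly for 24 doses per 6.3 and the schedule, with none at weeks 28 or 36. Limit item 10 at those two visits to accountability and return.
- **Minor wording:** change 25 doses to 24 in 3.3, and delete unblinded in 5.8.

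The cost is a text amendment; no new data, staff or patients are needed.
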